## Section 10.5 Statistical Methods

The statistical analysis plan will be developed and finalized before database lock and will describe the detailed analytical plans and procedures for *the* interim and final analyses, ~~performing sample size reassessments, interim and final analyses, and accounting for missing data.~~

## Section 10.6 Interim Analysis Analyses

There will be ~~1 up to 3~~ prespecified interim analyses analysis to assess *futility* the appropriateness of the planned sample size and efficacy. If the trial does not cross the pre-specified boundaries to declare early ~~efficacy or~~ futility at the interim *analysis* analyses, a final efficacy and safety analysis will occur after all participants complete the study Day 35 of follow-up.

A group sequential design strategy will be used to assess *futility* efficacy at each at *the* interim analysis. The ~~first and second analyses~~ interim *analysis* will occur after approximately 200 and 400 participants have completed Day 28 of follow-up.

~~The first interim analysis will occur after the first approximately 200 participants complete Day 28. At the first interim analysis, a sample size re assessment will be performed. The procedure for this blinded sample size reassessment will be detailed in the statistical analysis plan. In brief, the unblinded study statistician will assess the control event rate and drop out rate, and recalculate the sample size required to detect treatment effects of 35%, 40%, 45% and 50% with 80% statistical power using a 2.5% one-sided type I error rate. Based on this assessment, the~~

~~IDMC will make recommendations to the Sponsor for the final target sample size. This will be done with proper firewalls to maintain blinding of the information as it relates to the final target sample size.~~

~~If the final sample size is not adjusted, the first interim analysis for efficacy will also occur at this time and the second interim analysis will occur when approximately 400 participants complete Day 28. If the final sample size is adjusted at the first interim analysis, the first and second interim analyses for efficacy will occur when approximately one third and two thirds of the adjusted total number of participants complete Day 28.~~

### **Section 11.1 Independent Data Monitoring Committee**

The purpose of the IDMC is to monitor the study for safety and efficacy. ~~The IDMC will also review any sample size re-assessment analyses and recommend sample size changes as appropriate.~~

The IDMC will also review unblinded efficacy data at *a* pre-specified interim *analysis* analyses.

3. LIST OF ABBREVIATIONS AND DEFINITIONS OF TERMS

| | |
|-----------|---|
| AE | adverse event |
| AESI | adverse event of special interest |
| ANOVA | analysis of variance |
| ATC | anatomical therapeutic chemical |
| BMI | body mass index |
| CI | confidence interval |
| CMH | Cochran-Mantel-Haenszel |
| COPD | chronic obstructive pulmonary disease |
| COVID-19 | coronavirus disease 2019 |
| CRF | case report form |
| Ct | Cycle threshold |
| eCRF | electronic case report form |
| EOT | end of treatment |
| FDA | Food and Drug Administration |
| Gates MRI | Bill & Melinda Gates Medical Research Institute |
| IDMC | independent data monitoring committee |
| IEC | Independent Ethics Committee |
| IP | investigational product |
| ITT | intention to treat |
| LS | least squares |
| MedDRA | Medical Dictionary for Regulatory Activities |
| mITT | modified intention to treat |
| PCR | polymerase chain reaction |
| PI | principal investigator |
| PO | orally |
| PP | per protocol |
| PT | preferred term |
| SAE | serious adverse event |

| | |
|------------|---|
| SAP | statistical analysis plan |
| SARS-CoV-2 | severe acute respiratory syndrome coronavirus 2 |
| SD | standard deviation |
| SE | standard error |
| SoA | schedule of activities |
| SOC | system organ class |
| WHO | World Health Organization |

4. INTRODUCTION

The purpose of this statistical analysis plan is to describe the framework for the reporting, summarization and statistical analysis methodology of the safety and efficacy parameters measured for the Gates Medical Research Institute (MRI) study COD-01-T01-01. It is based on Protocol Gates MRI - COD-01-T01-01 Version 4, Amendment 2, 27 January 2021. This study is performed as part of an adaptive, randomized platform core protocol for treatment of early and mildly symptomatic individuals in out-patient settings with severe acute respiratory syndrome coronavirus 2 (SARS-CoV-2) infection. Additional statistical analysis plans will be developed for future protocols and interventions that will be added to the core protocol.

On January 28 and February 3, 2021, the Independent Data Monitoring Committee (IDMC) met to review the available safety and efficacy data to (1) perform the monthly safety review of accumulating data; and (2) evaluate the results of the first prespecified interim analysis for futility. Based on the review of the data, the IDMC determined on February 3, 2021, that the futility boundary was crossed and recommended that the clinical study be stopped. The final statistical analysis plan was amended to reflect changes to the planned analysis following early termination of the study.

As of February 4, 2021, the following changes were made in the study conduct:

- all randomization is ceased and no new study participants are enrolled.
- current participants must discontinue dosing of all study drug and discard their study drug.
- participants should remain in active, masked follow up and continue their study visits until Day 35 if they have had at least one dose of study drug.
 - Participants who have not reached Day 21 will continue safety follow up only until Day 35. These participants will be monitored for AEs, bleeding events and concomitant medication. These participants will not have further assessments for Gates MRI and WHO ordinal scale, symptoms, and nasal swabs for polymerase chain reaction (PCR) test.
 - Participants who have reached Day 21 but not Day 35 of study will continue safety and efficacy follow up until Day 35. These participants will be monitored for AEs, bleeding events, concomitant medication, Gates MRI and WHO ordinal scales, and symptoms. These participants will not have further nasal swabs for PCR test.
- participants who have not yet taken any study drug will discontinue the study early.

To address potential for substantial under-estimation of the treatment effect, efficacy analyses will be performed on a final efficacy analysis population as described in Section 7.1. Safety analyses will be performed on the Safety analysis population.

5 TRIAL OBJECTIVES

The following objectives and associated endpoints are part of this study.

Table 1: Study objectives and associated endpoints.

| Objectives | Endpoints |
|---|--|
| Primary | |
| To characterize safety of study intervention | Through Day 35 
 • Frequencies of grade 3 adverse events (AEs) and grade 4 AEs • AEs resulting in study intervention discontinuation • All SAEs |
| To assess efficacy of study intervention | 
 • Proportion of participants who progress to moderate or severe disease category or higher (Gates MRI ordinal scale ≥ 3) through Day 28 |
| Secondary | |
| To assess clinical efficacy of study intervention | 
 • Time to disease resolution, defined as symptoms resolution only (new onset COVID-19 symptoms resolved, and pre-existing symptoms returned to baseline*) through Day 28 • Time to disease resolution, defined as both viral clearance (two consecutive negative diagnostic tests) and symptoms resolution (new onset COVID-19 symptoms resolved, and pre-existing symptoms returned to baseline*) through Day 28. • Proportion of participants who progress to moderate or severe disease category or higher (Gates MRI ordinal scale ≥ 3) at Days 8, 14 and 21 • Proportion of participants who achieve disease resolution, defined as symptoms resolution only, at Days 8, 14, 21 and 28 • Proportion of participants who achieve disease resolution, defined as both viral clearance and symptoms resolution, at Days 8, 14, 21 and 28 • Gates MRI scale score at Days 8, 14, 21 and 28 • World Health Organization (WHO) ordinal scale score at Days 8, 14, 21 and 28 • Incidence and number of days of hospitalization at Days 8, 14, 21 and 28 |
| Exploratory | |
| To assess virological efficacy | 
 • Quantity (and change from baseline) of SARS CoV-2 virus at Days 8, 14, 21 and 28 |
| To assess viral sequence | 
 • Phylogenetic relationships of SARS-CoV-2 viruses sequenced from positive nasal swab samples |

*Baseline refers to health status prior to contracting new onset COVID-19 symptoms.

6 STUDY DESIGN CONSIDERATIONS

6.1 Study Design

This is an adaptive, randomized platform trial for treatment of early and mildly symptomatic individuals in out-patient settings with SARS-CoV-2 infection. The protocol will enroll people at high risk for COVID-19 progression based on age, BMI and comorbidity. The primary outcome through 28 days after the first intervention dose is focused on safety and efficacy (time to disease resolution or progression of disease).

Primary purpose: To assess the safety and clinical efficacy of a rivaroxaban with a primary endpoint of reduction in proportion of participants who progress to moderate or severe disease category or higher (Gates MRI ordinal scale ≥ 3) through Day 28.

Interventional model: Participants will be randomized 1:1 to either the rivaroxaban or the placebo group, in parallel for the duration of the study. Randomization will be stratified by site and by number of days since onset of symptoms at time of randomization.

Intervention groups:

Study intervention group: rivaroxaban, 10 mg (1 tablet) orally daily for 21 days.

Control group: placebo-equivalent (multi-vitamin supplement) 1 tablet orally daily for 21 days

Masking: Every effort will be made to mask the assigned treatment groups. Participants and study staff evaluating them will not be told of the assigned treatment groups. The laboratories performing the SARS-CoV-2 diagnostic testing will be blinded. Sponsor will be blinded throughout the study conduct.

Study visits: Every effort will be made to conduct the study protocol visits virtually with the study participants. A web-based video conferencing tool will be employed to allow for virtual (remote) interactions to take place between the study staff and the participant, for screening and all study visits.

Safety and efficacy monitoring: An Independent Data Monitoring Committee (IDMC) will be convened for this study for safety and efficacy monitoring with expertise in COVID-19 or respiratory viruses and emerging epidemics as well as biostatistics.

Changes in randomization strata: The protocol required an amendment after study start to address emergent and important issues at sites pertaining to screening and enrollment. The protocol amendment 1 modified the stratification factor of number of days since onset of symptoms at time of randomization by changing from <3 days vs. ≥ 3 days to <6 days vs. ≥ 6 days. Eight participants (1.3%) out of the total planned 600 participants randomized were enrolled under original protocol Gates MRI-COD-01-T01-01 Version 4 dated 01 August 2020 (randomized strata: <3 days vs. ≥ 3 days). Combining data from the original protocol and amendment 1 for the pre-specified analyses preserves the double-blind nature of the treatment comparison contrast in the same way a patient-level meta-analysis does. Because participants were randomly assigned under both protocols, one can expect participants within each treatment arm to be comparable at baseline under each of the original and amendment 1 protocols. Analyses where participants are analyzed according to the stratum to which they were randomized under the original protocol or protocol amendment 1 are statistically the most appropriate (resulting in 4 total stratification levels); however, the number of participants randomized under the original protocol (randomized strata: <3 days vs. ≥ 3 days) is relatively very small [8 (1.3%) out of the total planned 600 participants]. Further, since the number of participants randomized to the ≥ 3 days stratum is extremely small (2 participants) statistical modelling using a randomization factor with 4 stratification levels may not be possible. Because of this, and the fact that it is unlikely that knowledge of the protocol version will meaningfully impact investigators and participants e.g., with respect to participant management, follow-up or endpoint reporting, it is proposed that participants randomized under the original protocol are mapped under the new strata <6 days vs. ≥ 6 days and analyzed accordingly. Specifically, the 6

participants that were randomized to the <3 days strata will be assigned to the <6 days stratum and the 2 participants that were randomized to the ≥ 3 days stratum will be assigned to the <6 days vs ≥ 6 days according to the actual number of days since symptom onset at the time of randomization. As participants are not concurrently recruited for the two versions of the protocol and assignment to protocol version was not at random, analyses will be performed and reported separately for the original and amendment 1 protocols when possible to assess the similarity of the results.

6.2 Efficacy Measures

Efficacy measures include the following:

- Clinical status assessment using ordinal scale for Gates MRI
- COVID-19 symptoms
- Nasal sampling for SARS-Cov-2 diagnostic testing
- Clinical status assessment using ordinal scale for WHO

6.3 Safety Measures

Safety measures include AEs assessment, bleeding events and severity assessment.

7 STUDY POPULATIONS

7.1 Analysis Populations

An interim analysis was conducted on 28 January, 2021 using the data cut of 8 January, 2021. Efficacy interim analyses were produced based on the first 200 randomized participants who either had discontinued the study or had completed Day 28 in the ITT population. The interim efficacy primary endpoint result will be reported in the CSR using the data cut of 8 January, 2021.

IDMC's recommendation that the clinical study be stopped impacts the efficacy evaluation for the participants who were continuing in the study and had not yet reached Day 21 of the study (end of treatment period) as of 4 February, 2021. In order to have meaningful results of the final efficacy analyses, efficacy analyses will be performed on a final efficacy analysis set of participants who met either one the following criteria:

- Completed or discontinued the study or progressed prior to 5 February, 2021.
- Completed Day 21 or later visits as of 5 February, 2021.

Final analysis will be conducted following database lock.

- Efficacy analyses will be produced for randomized participants who meet the selection criteria described above and also meet the analysis population criteria described below.
- Safety analyses will be produced for all participants in the database who received at least one dose of study intervention.

Table 2: Analysis populations

| Population | Description |
|-------------------|--|
| ITT Population | All participants in the ITT population who met the criteria stated above. Participants will be analyzed according to the intervention to which they were randomized. |
| mITT population | All participants in the ITT population, who received the study intervention and have mild disease at study entry. Participants will be analyzed according to the intervention they actually received. |
| PP population | All participants in the ITT population, who received the study interventions as planned, have mild disease at study entry, and did not substantially deviate from the protocol procedures. Participants will be analyzed according to the intervention they actually received. |
| Safety population | All participants randomly assigned to study intervention, who received the study intervention. Participants will be analyzed according to the intervention they actually received. |

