## 2. Study Schedule of Procedures

**Table 1: Schedule of Activities**

Visits	Screening (≤5 days of Day 1)	Day 1	Day 4	Day 6	Day 8	Day 10	Day 12	Day 14	Day 18	Day 21	Day 24	Day 28	Day 35
Obtain consent	X												
Demographics, past and current medical history including known pregnancy/lactation status, and medication history	X												
Lab-confirmed SARS-CoV-2 positive diagnostic testing 	X												
Inclusion and exclusion criteria	X												
Concomitant medications	X	X	X	X	X	X	X	X	X	X	X	X	X
Randomization 	X												
Study intervention dose (Day 1 Day 21) and record adherence to dosing		X	X	X	X	X	X	X	X	X			
Clinical status assessment using ordinal scales for Gates MRI and WHO		X	X	X	X	X	X	X	X	X	X	X	X
COVID-19 signs and symptoms, temperature, oxygen saturation		X	X	X	X	X	X	X	X	X	X	X	X
AEs assessment	X	X	X	X	X	X	X	X	X	X	X	X	X
Bleeding events and severity assessment		X	X	X	X	X	X	X	X	X	X	X	X
Self-collection of nasal or oropharynx SARS-CoV-2 sample for diagnostic testing 	(X) 	X	X		X			X		X		X	

Note that visits will preferably take place remotely (refer to [Section 8](#)).

SARS-CoV-2= Severe acute respiratory syndrome coronavirus 2

Gates MRI= Bill & Melinda Gates Medical Research Institute

WHO = World Health Organization

 If there is documented positive SARS-CoV-2 diagnostic testing performed with a sample collected ≤10 days prior to screening, the test does not need to be performed. If no documentation, the potential participant will be asked to collect a nasal or oropharynx swab sample to send for testing.

 If documentation of a previous positive SARS-CoV-2 test is not available and a test is performed at screening, randomization will occur after a positive result is obtained.

 Participant will be asked to collect a sample per kit instructions. Discontinue collection during hospitalization and/or per physician's discretion when two consecutive negative results are available at any time during the study.

Note that an unscheduled visit may be required. Additional collection of a nasal swab sample may be performed based on the clinical judgement of the PI.

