**Table 9: Populations for Analysis**

Population	Description
Intention to treat (ITT) population	All participants randomly assigned to study intervention. Participants will be analyzed according to the intervention to which they were randomized.
Modified intention to treat (mITT) populations	All participants randomly assigned to study intervention, who received the study intervention and have mild disease at study entry. Participants will be analyzed according to the intervention they actually received.
Per Protocol (PP) population	All participants randomly assigned to study intervention, who received the study interventions as planned, have mild disease at study entry, and did not substantially deviate from the protocol procedures. Participants will be analyzed according to the intervention they actually received.
Safety population	All participants randomly assigned to study intervention, who received the study intervention. Participants will be analyzed according to the intervention they actually received.

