8 CHANGES IN CONDUCT OR PLANNED ANALYSES FROM THE PROTOCOL

Not applicable.

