9.2 General Conventions

Frequency (n) and percentages (%) will be used to summarize categorical variables; mean, standard deviation (SD), median, minimum, and maximum will be used to summarize continuous variables.

Decimal precision for summary statistics of continuous variables will be based on the mean value. Typically, the mean will contain 1 more decimal place than actual values but the decimal precision may vary in order to obtain an organized and understandable table or listing. The median will contain the same number of decimal places as the mean, the SD will contain 1 more decimal place than the mean, and the minimum and maximum will contain 1 less decimal place than the mean.

Unless otherwise specified, the denominators for percentages will be the number of participants in each intervention group with non-missing data for the variable of interest.

The day of receiving first dose of study intervention is defined as Study Day 1 or Day 1. All other study days will be computed relative to Day 1. For events on or after Day 1, study day for a particular event or visit will be calculated as $\text{Date}_{\text{event}} - \text{Date}_{\text{Day 1}} + 1$. For events before Day 1, study day for a particular event will be calculated as $\text{Date}_{\text{event}} - \text{Date}_{\text{Day 1}}$. Day 0 will not be used.

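### The final efficacy ITT set admits participants under Day 21 at the stop only if they progressed or discontinued, which biases both arms' progression rates upward

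*SAP*

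**What the plan says.** SAP 7.1 gives two alternative entry routes to the final efficacy set. The first is "Completed or discontinued the study or progressed prior to 5 February, 2021". The second is "Completed Day 21 or later visits as of 5 February, 2021". Table 2 of the SAP then defines the ITT population as "All participants in the ITT population who met the criteria stated above", and SAP 11.1.1 runs the primary analysis in it. The mITT and PP populations are subsets of the same set.

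Table 9 of the protocol defines ITT as "All participants randomly assigned to study intervention. Participants will be analyzed according to the intervention to which they were randomized". SAP section 8, which is reserved for changes from the protocol, reads "Not applicable".

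The SAP Introduction gives the reason for the restriction: "To address potential for substantial under-estimation of the treatment effect, efficacy analyses will be performed on a final efficacy analysis population". It also says what happens after 4 February 2021. Dosed participants under Day 21 stay in the study for safety follow-up to Day 35 but have no further ordinal-scale assessments. Participants not yet dosed leave the study.

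**The concern.** Take two dosed participants randomised on the same day, both under Day 21 at the stop. If one has progressed, that person enters the set as an event. If the other has not progressed and remains in safety follow-up, that person has neither completed, discontinued, progressed nor reached Day 21, and is excluded. Among participants with short follow-up, the set keeps the events and drops most of the non-events.

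The reported Day 28 risks would then describe no group defined by randomisation. The mITT, PP and actual-strata sensitivity analyses cannot reveal this because they sit inside the same set, and the SAP version history shows that sensitivity analyses 1 to 3 of the primary endpoint were dropped. At stake are the absolute progression rates and the risk difference that readers will take from a trial stopped for futility.

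**Working it through.** **The plan's own figure.** SAP 9.1.1 assumes 30% against 19.5%, one-sided 2.5%, 80% power and 10% drop-out. The pooled-variance formula gives 264 evaluable per group, and 264/0.9 = 293.3, rounded up to 294. This matches the SAP, so its design rates are used below.

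**Inputs.** From the documents: p = 0.30 (control) and 0.195 (rivaroxaban); 0.35 against 0.30 from the first harm scenario in SAP 11.5.1.1. Assumed, because the documents do not give them:
- Nf participants with full follow-up and Ny under Day 21 at the stop, both arms together: 400+50, 400+100 or 350+150
- f, the share of eventual events seen by the stop: 0.5 or 0.7
- q, the share of under-Day-21 non-progressors who discontinued and are carried forward as not progressed: 0 to 0.10

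**Formula.** Expected proportion under the SAP rule = (Nf·p + Ny·p·f) / (Nf + Ny·p·f + Ny·(1 − p·f)·q). Only the ratio of Nf to Ny matters, so the combined counts serve for each arm.

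| Nf+Ny, f, q | Control | Rivaroxaban | Difference | Ratio |
|---|---|---|---|---|
| 400+50, 0.5, 0.10 | 127.5/411.75 = 30.97% | 82.875/409.39 = 20.24% | -10.72 | 0.654 |
| 400+100, 0.7, 0.10 | 141/428.9 = 32.87% | 91.65/422.29 = 21.70% | -11.17 | 0.660 |
| 350+150, 0.7, 0 | 136.5/381.5 = 35.78% | 88.725/370.48 = 23.95% | -11.83 | 0.669 |

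Over the whole grid, control is 31.0-35.8% (truth 30%) and rivaroxaban 20.2-24.0% (truth 19.5%). The difference is -10.7 to -11.8 points (truth -10.5) and the ratio 0.654-0.669 (truth 0.650).

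**Wider grid.** With 10-40% of each arm under Day 21, f = 0.3-0.7 and q = 0-0.10, control is 30.4-38.6%, rivaroxaban 19.8-26.2%, and the difference -10.6 to -12.4 points. Every cell lies above the truth in both arms.

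**Break-even.** The bias vanishes at q = f(1 − p)/(1 − p·f). With p = 0.30 and f = 0.5 this is 0.35/0.85 = 41%; with p = 0.195 and f = 0.7 it is 0.5635/0.8635 = 65%. At f = 0.3 it is 23-26%. The planned drop-out is 10%.

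**Harm scenario.** The difference moves from +5.0 to between +5.1 and +5.4 points, and the ratio from 1.167 to 1.151-1.163.

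**Null case.** With both arms at 30% or both at 15% and the same timing, the mean difference is within 0.02 points of zero. The one-sided rejection rate is 2.3-2.6% (200,000 replicates per scenario, unstratified Miettinen-Nurminen score test).

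**Unequal timing.** With both risks 30% but f = 0.7 in control and 0.5 in rivaroxaban, a false difference of -0.5 to -1.6 points appears. For example, at 400+50 and q = 0: 127.5/407.5 − 130.5/410.5 = 31.29% − 31.79%.

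**Undosed participants.** Intercurrent-event rule 4 in SAP 11.1.1 counts anyone who leaves before dosing with no scale assessment as progressed. Participants left undosed by the stop can therefore enter as discontinued and become imputed events. At 400+100, f = 0.5, q = 0.10, with an assumed 10% of the under-Day-21 group undosed: control is (120 + 13.5 + 10)/431.15 = 33.3%, rivaroxaban (78 + 8.775 + 10)/426.90 = 22.7%, difference -10.6 points, ratio 0.681. Without this rule the same case gives 135/423.5 = 31.9% and 87.75/418.78 = 21.0%.

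**The case against.** The strongest reply is that the comparison is little affected. With equal rates and timing there is no bias and no excess type I error. The overstated benefit needs the full design effect to be true, in a trial that crossed a futility boundary. In the harm scenario the shift is at most 0.4 points. The unequal-timing case rests on a contrast that no document supports. All of this stands, and it confines the main harm to the absolute rates and, when a true effect exists, the risk difference.

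The size is also assumed. If only 30% of events were seen by the stop, the smallest control excess falls to about 0.4 points and break-even to 23-26% discontinuing. The main grid also leaves out rule 4, which raises the absolute rates further but reduces the exaggeration of the difference. These points change the size. They do not change the direction at the planned 10% drop-out.

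The restricted set is openly described in the SAP Introduction, section 7.1 and the version history. The disclosure gap is therefore a missing section 8 entry, not concealment. The interim result, to be reported from the 8 January cut, has no entry route through progression. It covers only the first 200 participants and is not a sensitivity analysis of the final set.

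**Conclusion.** The concern holds. As written, entry for dosed participants under Day 21 depends on the primary outcome or on discontinuation, and every efficacy population inherits this. Under the stated assumptions the control rate is 1.0-5.8 points too high. At the design effect the risk difference is 2-13% too large, while the risk ratio moves slightly toward 1. The number under Day 21, the timing of events and the discontinuation rate are not in the documents, so the size cannot be fixed; the upward direction holds unless discontinuation far exceeds the plan. The test under equal rates and timing is sound. This should be fixed because the published absolute risks would be distorted and the repair needs no new data.

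**What to change.** 1. Define the final efficacy set by randomisation date only, and delete both the progressed and the discontinued entry routes. SAP 9.2 states "The day of receiving first dose of study intervention is defined as Study Day 1 or Day 1", and the protocol's schedule allows up to 5 days from screening to Day 1. With a 5-day allowance the cutoff is 10 January 2021 (10 January + 5 + 20 days = 4 February). Include everyone randomised by then, whatever their outcome, discontinuation or dosing status. This still meets the SAP's aim of leaving out immature follow-up. A different allowance would move the date; what matters is that the outcome plays no part.
2. Add a sensitivity analysis: the Day 28 Kaplan-Meier risk difference in all randomised participants, timed from randomisation, with non-progressors under Day 21 censored at the stop. Censor participants left undosed because of the stop; do not count them as progressed under rule 4.
3. Record the departure from the protocol's ITT definition in SAP section 8.
4. Reconcile SAP 11.5.1, which says enrolled participants are followed to study completion after a futility stop, with the SAP Introduction, which ends ordinal-scale assessment for those under Day 21.

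In simulation (6,000 replicates, true risks 30% and 19.5%) the date-only set and Kaplan-Meier each gave 29.9-30.1% and 19.5-19.6%, against 31.3-36.3% and 20.5-24.3% under the SAP rule. A second simulation with 10% drop-out gave 29.3-29.4% for control in the date-only set. That small shortfall comes from carrying the last observation forward; Kaplan-Meier gave 30.0%.

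The cost is SAP wording, one date flag, one extra analysis and some precision. At 400+100 the SD of the difference is about 4.2 points for the date-only set and 3.9 for Kaplan-Meier. The 4.2 appears not to include the loss of participants randomised after 10 January who were dosed quickly and reached Day 21. In the second simulation, with 20% under Day 21 and the design effect true, the chance of a significant result was 74.5% in the date-only set against 80.3% under the SAP rule. Participants who leave the main set remain in the Kaplan-Meier analysis.
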